10.6.9. End of Study

Patients will undergo the following assessments and procedures at End of Study:

- Concomitant medication review (ongoing)
- Assess AEs, SAEs, and potential clinical endpoints (ongoing)
- Weight
- Vital signs
- 12-lead ECG
- PE
- Central clinical laboratory evaluations:
 - Hematology, blood chemistry, and urinalysis
 - Basic fasting lipids (TC, calculated LDL-C, HDL-C, non-HDL-C, and TGs)
 - hs-CRP
 - HbA_{1C}
- Return of IMP; assessment and recording of IMP adherence
- Diet and exercise counselling

Note: The conduct of this visit may be altered to ensure patient safety during the global COVID-19 pandemic. If permitted and approved by regional regulatory authorities and the appropriate IRB/IEC, this visit may be converted to a remote visit (telephone, telemedicine, etc.) or conducted within the patient's home by a qualified visiting nurse. However, at a minimum, it is expected that the following data be collected regardless of whether the visits is conducted by phone or by visiting nurse: concomitant medications, assessment of AEs, SAEs, and clinical endpoints, and IMP adherence. When visits are conducted in the patient's home by a qualified visiting nurse, it is also expected, if logistically possible, that weight, vital signs, and samples for central laboratory evaluations will also be collected. Alterations to study visits and procedures during the pandemic will be recorded on a COVID-19-specific case report form.

Local laboratories may be utilized during the pandemic at the investigator's discretion with the following requirements:

- Lipids should not be assessed by local laboratories during the study. However, if lipids are included in a local laboratory report, care must be taken to ensure that the values remain masked for study site personnel, the patient, CRO, and Sponsor.
- A copy of the lab results and reference ranges, with lipid results redacted, must be filed within the patient records.

In individual cases after the pandemic has been determined to be over and if permitted and approved by regional regulatory authorities and the appropriate IRB/IEC, this visit may be conducted within the patient's home by a qualified visiting nurse.

10.6.10. Post-treatment Visit (Phone Visit; Visit PT1, 30 days ± 10 days After End of Study)

Patients will undergo the following assessments via telephone 30 days after the end of study:

- Assess AEs, SAEs, and potential clinical endpoints

10.7. Discontinuations

10.7.1. Patients Inadvertently Enrolled

The inclusion and exclusion criteria for enrollment must be followed exactly and completely. If a patient who does not meet enrollment criteria is inadvertently enrolled, the Medical Monitor should be contacted within 24 hours of identification. If it is determined after discussion with the Medical Monitor that, in considering patient safety, it is appropriate to continue IMP (documentation of this is necessary), the patient will continue on IMP and be monitored for all visits and testing (including laboratory measures) for the duration of the study. If, after discussion with the Medical Monitor, it is determined that the patient should not continue IMP, IMP will be discontinued, but the patient will remain in the study to be evaluated for concomitant medications, and efficacy and safety endpoints until the end of the study visit.

Patients inadvertently enrolled under the following criteria should be discontinued from IMP (but remain in the study):

- Female patients who are pregnant or are breastfeeding or who do not agree to use an acceptable method(s) of birth control during the study
- Any clinically significant medical condition that according to the investigator could interfere with participation in the study
- Unable or unwilling to comply with protocol requirements, or deemed by the investigator to be unfit for the study
- Have a history of drug, alcohol, or substance abuse within the past 6 months, as assessed by the investigator

If a patient stops IMP for any of the above exclusion criteria following discussion with the Medical Monitor, then investigators should notify the Sponsor (or designee). The reason for the patient's inadvertent enrollment should be documented in the patient's record.

10.7.2. Temporary Discontinuation of Investigational Medicinal Product

There may be situations in which IMP is temporarily discontinued at the discretion of the investigator. IMP should be restarted as soon as possible based on investigator judgment. The number of days the IMP was not taken and the reason for temporary discontinuation should be documented in the patient's record. There is no limit to the amount of time patient can be off IMP prior to restarting.

Investigators should contact the Medical Monitor if IMP is temporarily discontinued and this should occur prior to IMP discontinuation if possible.

10.7.3. Permanent Discontinuation of Investigational Medicinal Product

There may be situations where it may be necessary for a patient to permanently discontinue IMP.

Investigators should contact the Medical Monitor prior to permanent IMP discontinuation to discuss the situation. **If IMP is permanently discontinued, the patient will remain in the study to be evaluated for concomitant medications, efficacy and safety endpoints until the final study visit.** If the patient is unwilling or unable to return for follow-up visits in person, alternatives such as telephone contact visits per the Schedule of Events, or telephone follow up bi-annually, annually or at the end of the study will be offered. The follow-up frequency will be documented in the eCRF.

The reason for permanent discontinuation of IMP should be documented in the eCRF. If the discontinuation of IMP is due to an AE, the event should be documented in the eCRF. Some possible reasons that must lead to permanent early IMP discontinuation include:

- Female patients who become pregnant or are breastfeeding or who do not agree to use an acceptable method(s) of birth control during the study will be permanently discontinued from IMP
- The patient requests to stop IMP permanently
- The patient study blind is broken
- Patient moves away and it is impossible to come to this or any other trial site for visits as required by protocol.

Some possible reasons that may lead to permanent early IMP discontinuation include:

- In the opinion of the investigator, any AE or a significant change in a laboratory value that warrants permanent discontinuation of IMP therapy. Investigators are advised to call the Medical Monitor prior to making such a decision.
- Illness, condition, or procedural complication (including AEs) affecting the patient's ability to participate or requiring prohibited medication. Investigators are advised to call the Medical Monitor prior to making such a decision.
- Enrollment in any other clinical trial involving an investigational product or enrollment in any other type of medical research judged not to be scientifically or medically compatible with this study. If, after discussion with the study Medical Monitor, it is determined that the patient should not continue IMP, IMP will be discontinued.

10.7.4. Patient Discontinuation from the Study

Patient discontinuation prior to the patient's completion of the study is expected to be uncommon, occurring only if the patient explicitly withdraws consent. At the time of discontinuing from the study, the Medical Monitor should be contacted, and, if possible, an early discontinuation visit should be conducted, per the Study Schedule. The patient will be

permanently discontinued both from the IMP and from the study at that time. During the study closeout period, survival (vital) status will be collected within legal and ethical boundaries for all patients randomized who withdrew their participation from the study.

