4.3. Study Closeout

The study will continue until all the following criteria have been met:

1. at least 1,620 patients have experienced an adjudicated primary 4-component MACE (CV death, nonfatal MI, nonfatal stroke, or coronary revascularization),
2. at least 810 patients have experienced an adjudicated 3-component MACE (CV death, nonfatal MI, or nonfatal stroke) and
3. 24 months have elapsed since the last patient was randomized.

During the study closeout period (when the patients' End of Study (EOS) Visits will be scheduled), each patient still in the study will be required to complete an in-clinic visit which is

designated as the EOS Visit and perform the procedures according to Protocol Appendix 1, Schedule of Events. Patients who are still on IMP at the visit will be asked to end study treatment.

A post-treatment telephone visit will occur 30 days (\pm 10 days) after the EOS visit to assess AEs, SAEs and identify potential clinical endpoints.

[figure not shown]
During the study closeout period, vital status will be collected within legal and ethical boundaries (see Protocol Section 10.7.5) for all patients who did not complete the study, and only those with unknown status are considered as lost to follow-up.

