7.2. Key Study Dates

7.2.1. Definition and Imputation of Key Event Dates

Date of End of Study (EOS): the study completion/early termination date recorded on the “Study Completion/Early Termination” CRF. Note that the patient may have a 30-day post EOS follow-up visit after this.

Date of Study Completion (DSC): For patients who did not complete the study, it is the later of a) the date of EOS and b) the date of the 30-day post EOS follow-up visit. For patients who completed the study, it is the latest date of a) the date of EOS, b) the date of the 30-day post EOS follow-up visit, or c) the date of death. This date is used to calculate the duration of study (follow-up) for each patient and all clinical events that happen during this period are adjudicated.

Date of First Dose of IMP (DFDOSE): for each patient, the DFDOSE is the date/time of administration recorded on the “On-Site Study Medication/ Compliance” CRF at Visit T1. If that field is missing, it is set to be next first date of administration at Visit T3.

Date of Last Dose of IMP (DLDOSE): the date of last dose is recorded on the End of Treatment CRF. In cases of missing either completely or partially, it is imputed as the earliest date of a) the last day of the month (if the month and year are present), or the last day of the year (if only the year is present); b) the Date of EOS; and c) the date of the last IMP dispense plus the number of tablets taken.

Date of Last Visit (DLVISIT): the last date recorded on either the *Visit Date* or the *Telephone Contact* CRFs. For patients who did not complete the study, this must be on or prior to the DSC.

Date of Last Known Alive (DALIVE): for patients whose vital status at the end of study is either alive or unknown, this is the last day when the patient is known to be alive. It is the latest “last known alive date” recorded on the *Survival Status* CRF. If this date is partially or completely missing, it is set to the later of last known alive date with imputation and DSC.

Date of Last Assessment for Non-Fatal Clinical Endpoints (DLASMT): Potential clinical endpoints are assessed every three months either in clinic or by telephone through the Post-EOS Phone visit. For patients who died during the study within 90 days of last visit, the DLASMT is set to the date of death. Otherwise, the DLASMT is set to be DLVISIT. Note that this definition also applies to new-onset diabetes mellitus (NODM) as an efficacy endpoint.

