Date of Last Survival Follow-Up (DLSFU): For patients who completed the study, or withdrew consent, or discontinued study and were identified as dead only through survival search (death is not adjudicated), it is the DSC. For all other patients it is the Date of Last Known Alive. This is the last date for survival status follow-up.

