7.2.5. Time to Event and Date of Censoring

For time-to-event analysis of clinical endpoint events (including new-onset type 2 diabetes), the start date is the date of randomization when the FAS is used, based on the ITT principle. When the PPS is used, the start date is set to be the date of first dose. For composite endpoints, the event date is the date of the first component event.

Patients who did not have any event in question will be considered as censored for the analysis. The date of censoring is determined as the following:

- Fatal events (CV death, fatal MI, fatal stroke, all-cause mortality): censored at Date of Last Survival Follow-Up.
- Non-fatal events and composite endpoints that include both fatal and non-fatal events: censored at the Date of Last Assessment.

Please see Section 18.3 for special censoring rule as applicable to patients from Ukraine as a result of the ongoing conflict.

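### Vital status lawfully collected at closeout for patients who withdrew consent is left out of the confirmatory all-cause mortality analysis

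*Protocol*

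**What the plan says.** **Collection.** Protocol 10.7.4 provides that during closeout "survival (vital) status will be collected within legal and ethical boundaries for all patients randomized who withdrew their participation from the study". SAP 4.3 has vital status collected, where lawful, "for all patients who did not complete the study, and only those with unknown status are considered as lost to follow-up".

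**Analysis.** SAP 7.2.5 gives the rule for mortality endpoints: "Fatal events (CV death, fatal MI, fatal stroke, all-cause mortality): censored at Date of Last Survival Follow-Up". SAP 7.2.1 sets that date by group. "For patients who completed the study, or withdrew consent, or discontinued study and were identified as dead only through survival search", it is the Date of Study Completion (DSC), and a parenthesis notes that a death found this way is not adjudicated. "For all other patients it is the Date of Last Known Alive". For a patient who did not complete the study, the DSC is defined thus: "it is the later of a) the date of EOS and b) the date of the 30-day post EOS follow-up visit". Date of death is an option in the DSC only for completers.

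**Events.** SAP 15.1 derives the endpoints from positively adjudicated events after randomization. SAP 8.5 likewise treats every clinical endpoint and its date as adjudicated.

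**Role of the endpoint.** All-cause mortality is step 7, the last, of the alpha-controlled hierarchy (SAP 8.3; Protocol 15.7).

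**The concern.** All-cause mortality needs a date of death and no adjudicated cause. It is the one endpoint for which a closeout vital-status search can supply what is needed for a patient who has refused further contact. Protocol 10.7.4 expects patients to leave the study only by explicit withdrawal of consent, so withdrawers are the main group that the search serves. Yet what it finds does not reach the step 7 test.

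Two things are at stake. Some known deaths and some known survival time are discarded. The test also then assumes that, within each arm, patients who withdrew have the same later mortality as those who stayed. That assumption could fail if some withdraw because of illness or an adverse event. The multiple-imputation and tipping-point analyses (SAP 15.2.4 and Appendix 6) address this kind of assumption for MACE-4 only. The per-protocol analysis (SAP 15.4.1) repeats the same methodology.

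**Working it through.** **1. Tracing the rule for a consent-withdrawer**

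- All-cause mortality is censored at the Date of Last Survival Follow-Up (SAP 7.2.5).
- For a withdrawer that date is the DSC, with no condition on vital status (SAP 7.2.1).
- The DSC of a non-completer is the exit date, or the 30-day contact if later (SAP 7.2.1).
- Deaths within 30 days of discontinuation go to adjudication (Protocol 13.2.6) and can count. A later death found only by the search is not adjudicated, so SAP 15.1 does not make it an event.
- Found dead after the window: censored at the DSC, no event. Found alive: censored at the DSC, no added follow-up.

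The sentence in SAP 7.2.1 could also be parsed so that the search-only condition covers withdrawers too. The deaths are still dropped on that reading, so the result does not depend on it.

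**2. Size**

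The plan gives no figure for deaths, consent withdrawals or the power of the mortality test. Its one event target, 1,620 MACE-4 events, reproduces: Schoenfeld 4 × (1.960 + 1.282)² / (ln 0.85)² ≈ 1,592, and Freedman 1,599. It has no bearing on this point. The only attrition figure is loss to follow-up of 1% per year (Protocol 15.2; SAP 8.1), which is not a withdrawal rate.

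From the documents: N = 14,000 and average follow-up T = 3.5 years. Assumed: withdrawal w of 0.25% to 2% per year, mortality m of 1% to 3% per year, mortality after withdrawal k × m with k = 1 or 2, constant hazards, and every death traced.

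- Counted deaths = N × m/(w+m) × (1 − e^(−(w+m)T))
- Dropped deaths = N × ∫₀ᵀ w e^(−(w+m)t) (1 − e^(−km(T−t))) dt

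| w per year | m per year | k | Counted | Dropped | Dropped, % of all deaths |
|---|---|---|---|---|---|
| 0.25% | 1% | 1 | 479 | 2.1 | 0.43 |
| 1% | 2% | 1 | 930 | 16.2 | 1.71 |
| 1% | 2% | 2 | 930 | 31.6 | 3.29 |
| 2% | 1% | 2 | 465 | 32.4 | 6.51 |
| 2% | 3% | 2 | 1,349 | 90.6 | 6.30 |

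A hand check of the second row, ignoring attrition: N × w × k × m × T²/2 = 14,000 × 0.01 × 1 × 0.02 × 6.125 = 17.2, close to 16.2.

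A cruder calculation assumes that 2% to 6% of patients withdraw, with 1.5 to 2.5 years remaining and mortality of 1.5% to 2% per year. It gives 14,000 × 0.02 × 1.5 × 0.015 = 6.3 to 14,000 × 0.06 × 2.5 × 0.02 = 42 dropped deaths. Set against 14,000 × 3.5 × 0.015 = 735 to 14,000 × 3.5 × 0.02 = 980 deaths in all, that is 0.9% to 4.3%.

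For given rates the model figures are upper bounds. Tracing will not be complete, and the model counts deaths as dropped from the day of withdrawal, not from the end of the 30-day window.

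**3. Loss of precision**

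The standard error of the log hazard ratio varies roughly as 1/√deaths. Dropping a share p inflates it by 1/√(1−p): 1.002 at 0.43%, 1.009 at 1.71% and 1.034 at 6.51%.

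**The case against.** **The Protocol does the same.** A reader might infer that the SAP overrides a Protocol commitment. It does not. Protocol 10.7.4 says that vital status is collected, not that it enters the mortality test. Protocol 15.6 censors withdrawers when consent is withdrawn, and 15.7.1 carries similar censoring to the secondary endpoints. This objection stands against any claim of conflict. It does not show that the data should go unused. The rule in 15.6 is written for MACE, where nonfatal events cannot be assessed in someone who refuses contact, and a vital-status search removes that obstacle for death.

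**The rule is symmetric.** On the plain reading of SAP 7.2.1, withdrawers found dead and found alive are treated alike, so censoring does not depend on outcome. This stands. The uneven part of that sentence concerns other discontinued patients: those found dead only by search are cut back to the DSC, while those found alive run to the Date of Last Known Alive. That is a separate matter.

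**Not all deaths are lost or hidden.** This also stands. Deaths within 30 days of discontinuation are adjudicated, and SAP 9 summarizes and lists final survival status for the FAS.

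**Using the search could introduce its own bias.** If deaths are easier to trace than survivors, ascertainment depends on outcome, which the present rule avoids. This is a real cost. It is a reason to show both analyses and to report how complete tracing was.

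**Limited reach.** Step 7 is last, so no other test depends on it. The SAP invokes intention-to-treat to name the FAS and to set the start date, and it does not promise survival follow-up to a common date after withdrawal. Both points are fair.

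**Conclusion.** The concern holds as one of unused data. Vital status that the plan sets out to collect for withdrawers does not enter the step 7 mortality test. Nor does it enter any mortality sensitivity analysis in the SAP text available. The contents list a Section 18.4 on sensitivity analyses of the primary and key secondary endpoints, under the Ukraine heading. Its text was not available, so an analysis there cannot be excluded.

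A reader might go further and infer that the mortality result is biased. The documents do not support that. Bias needs withdrawal to be informative, and nothing in the plan shows that it is or how it would differ by arm. No effect on the hazard ratio or the type I error has been shown. What is certain is some loss of information: about 2 to 91 deaths, or 0.4% to 6.5%, under the assumed rates and full tracing. That is modest. It would matter most if the mortality result were borderline or withdrawal differed between arms.

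**What to change.** For all-cause mortality only, amend SAP 7.2.1, 7.2.5, 8.5 and 15.1, before database lock and unblinding, so that:

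- any dated death found by lawful vital-status collection counts as an event on its date, whether or not it was adjudicated;
- traced survivors are censored at the Date of Last Known Alive;
- untraced patients stay censored at the DSC.

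Report the analysis under the present rule alongside it, and tabulate tracing completeness by arm. If the sponsor keeps the present rule as confirmatory, prespecify the vital-status analysis as a sensitivity analysis. Leave CV death and the other cause-specific deaths unchanged. Reword the sentence on the Date of Last Survival Follow-Up so that it can be read in only one way.

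**Cost.** Wording in four SAP sections, one derivation and one extra table. SAP 7.2.1 cites the Survival Status CRF for the last date known alive but does not say that it records a date of death for search-found deaths, so this must be confirmed. Step 7 would include some deaths that cannot appear in step 6. Tracing will be incomplete where it is not lawful, and deaths may be easier to trace than survivors.

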10.7.5. Patients Lost to Follow-Up

A patient would be considered potentially lost to follow-up if he or she repeatedly fails to return for scheduled visits and is unable to be contacted by the study site. Site personnel are expected to make diligent attempts to contact patients who fail to return for a scheduled visit or were otherwise unable to be followed up by the site. Refer to the Retention Guide for additional details. Vital status will be collected within legal and ethical boundaries during the study closeout period. If vital status is determined, the patient will not be considered lost to follow-up.

10.7.6. Discontinuation of Study Sites or the Study

The Sponsor may suspend enrollment or discontinue a site at any time. A written statement will be provided to the investigator, the IRB or IEC, and regulatory authorities, if required.

Possible reasons for site discontinuation include, but are not limited to:

- Unsatisfactory enrollment with respect to quantity or quality
- Inaccurate or incomplete data collection on a chronic basis
- Falsification of records
- Failure to adhere to the protocol
- Lack of study oversight by the Principal Investigator and/or designee

If any serious or nonserious AEs have occurred at such a clinical site, all documentation relating to the event(s) must be obtained.

The Sponsor in consultation with the EC Chair will retain responsibility for discontinuation of the study. The study will be discontinued if necessary for medical, safety, regulatory, or other reasons consistent with applicable laws, regulations, and Good Clinical Practice (GCP).

Discontinuation of the study may be based on a recommendation from the DMC. The criteria that the DMC will follow to recommend early termination the study will be described in the DMC Charter.

11. ASSESSMENT OF EFFICACY

11.1. Reporting of Clinical Endpoints

All clinical endpoints occurring at any point from signing the ICD until 30 days after completion of the study will be reported by the site and adjudicated by the CEC according to guidelines detailed in the CEC Charter. Study sites will complete the relevant clinical endpoint eCRFs and obtain other required source documents in a timely fashion as per study-specific instructions contained in the Endpoint Manual.

Clinical endpoints include any of the following:

- CV Death (MACE)
- Non-CV Death (non-MACE clinical endpoint)
- Nonfatal MI (MACE)
- Nonfatal stroke (MACE)
- Hospitalization for unstable angina (non-MACE clinical endpoint)
- Coronary revascularization (MACE)

Detailed definitions of these clinical endpoints are included in the CEC Charter and the Endpoint Manual. Please note that the Sponsor will also review blinded AE and SAE reports on a routine basis in order to identify potential additional clinical endpoints. AEs and SAEs that are identified by the Sponsor as potential clinical endpoints will be reviewed by the CEC and may result in a request to the site that additional source documentation be obtained or adjustments to reporting in the eCRF be completed.

An adjudicated clinical endpoint will not be reported as an AE nor, if appropriate, as an SAE in the eCRF. Additionally, it will NOT be reported in an expedited manner as an SAE since these events are expected to occur in this patient population.

A clinical endpoint that is reported by the site but, upon subsequent review by the CEC is adjudicated to NOT meet all of the clinical endpoint criteria as defined by the CEC Charter, will be reclassified as an AE, SAE, or procedure as appropriate. If that reclassified event meets one or more of the seriousness criteria for AEs, the event must be reported (within 24 hours of notification of investigator) as an SAE in the same manner as other SAEs. In this instance, Day 1 for SAE reporting purposes will be the day that the investigator is informed that the reported clinical endpoint did not meet clinical endpoint criteria adjudicated by the CEC. At the time that a clinical endpoint is reported, information will also be collected that would be required if, in the future, it is determined to be an SAE. This information will include AE term, severity, action taken with IMP, relatedness, etc.

Any clinical endpoint occurring after the 30-day follow-up period that the investigator becomes aware of and considers related to IMP must be reported to the Sponsor as an SAE.

Please contact your monitor regarding any questions about the reporting of clinical endpoints and whether these clinical endpoints should be reported as AEs and/or SAEs.

